- Précis:** Pilot trial designed with a two part aim at enrollment. Aim 1 is designed as a randomized, controlled trial for older patients (≥ 75 years) who are indicated for CRT device implantation to receive a CRT-P or CRT-D. Information collected will help to assess the ability to enroll and retain older patients in a randomized controlled trial of CRT-P versus CRT-D in preparation for a large pivotal trial. Aim 2 is a non-randomized, observational study of patients who were offered inclusion into Aim 1 but refused to participate. Aim 2 subjects present an opportunity to understand the reasons why older patients may refuse enrollment into a randomized trial as well as still allowing for collection of data regarding their chosen CRT device.
- Objectives:** **Primary Objective:** Feasibility of enrolling and maintaining elderly heart failure patient in CRT-P vs CRT-D randomized trial.
Secondary Objectives: Examine predictors of refusing randomization and of choosing CRT-P vs. CRT-D device implantation in elderly patients.
- Endpoint** **Primary Endpoint:** The ability to enroll in the randomized controlled trial of CRT-P versus CRT-D patients.
Secondary Endpoints: Determinants of refusing participation in CRT-P versus CRT-D clinical trial.
- Population:** Patients 75 years or older who are clinically indicated for CRT device implantation based on published guidelines⁶ will be considered for this trial. The racial, gender, and ethnic characteristics of the proposed subject population represent the populations cared for at the participating institutions. Subjects meeting all inclusion and none of the exclusion criteria for Aims 1 and 2 will be enrolled in this research. No exclusion criteria shall be based on race, gender, or HIV status. Patients younger than 75 years of age are excluded based on study rationale and design.
- Study Type:** Pilot trial with two clinical Aims. Aim 1 is a randomized clinical trial and Aim 2 is an Observational clinical trial.
- Number of Sites**
Enrolling Participants: Total of four participating sites
- Study Duration:** Approximately 24 months
- Participant Duration:** Up to 18 months from enrollment

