6 STUDY PROCEDURES AND SCHEDULE

Randomization Aim

Table 1 details the baseline data collected for every enrolled patient. Baseline demographics (e.g. age, gender, and race) and clinical information (e.g. cardiac condition, comorbid conditions, echocardiographic parameters, EKG parameters) will be abstracted from the electronic medical records of each participating institution. QOL questionnaires will be obtained at enrollment and at the 6-month follow-up visit using both the RAND-36 health Status Inventory³⁵ and the Minnesota Living with Heart Failure Questionnaire³⁶. A paper and pencil option will be provided unless the patient is unable to read or write in which case the questionnaires will be administered verbally by a research coordinator.

Patients will be followed in the pilot randomized trial from the date of enrollment until study closure. During follow-up, information will be collected on procedural details and complications, as well as clinical events including death, hospitalizations, and emergency room visits. The events will be ascertained by asking the patient or their caregiver. Data pertaining to hospitalizations and emergency room visits will be readily available if they occurred at the enrolling institution. If at another institution, these data will be collected by asking the patient to sign a release of medical records form and by obtaining relevant clinical information from the other institution. The cause of death and primary reason for hospitalization will be adjudicated as cardiac (arrhythmic or non-arrhythmic) or non-cardiac by an adjudication committee that is independent from the research team. For the CRT-D arm of the study, information about appropriate and inappropriate device shocks and anti-tachycardia pacing therapies will be collected. Importantly, rates of patient screening, enrollment, randomization, and retention in the study will also be collected.

Table 1. Baseline Data	Variables Collected
Demographic variables	Age, Gender, Ethnic background, type of insurance (primary and secondary), Zip code

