The milestones of data collection are detailed in Table 2. Patients enrolled in the randomized pilot trial will have baseline demographic, clinical, and pharmacological information collected after they sign written informed consent. QOL questionnaires and patient satisfaction will also be obtained at baseline. At the scheduled date of device implantation, which will be within 30 days of enrollment, procedural details will be collected including total and fluoroscopic durations of the procedure, device and lead models, and any acute major or minor procedural complications. Patients whose device implantation procedure is scheduled > 30 days from the date of enrollment have to be re-consented for participation in this trial. In follow-up, each patient will be contacted by phone at 30 days, 3 months, and 6 months post enrollment and every 6 months thereafter until the end of the study. The phone calls will be used to collect interim information from patients or next of kin regarding non-acute procedural complications or clinical events (e.g. death, hospitalization). Original medical records will be obtained for all clinical events and will be reviewed by an independent adjudication committee. Each scheduled phone visit will also be associated with a remote device interrogation to assess device function and obtain information about stored arrhythmic events.

Observational Aim

Patients enrolled in the observational cohort of Aim 2 will have demographic and clinical data collected at baseline similarly to patients enrolled in the randomized trial of Aim 1. Table 1 details the clinical variables collected at enrollment. Table 2 details the follow-up milestones. Also, patients enrolled in Aim 2 of this proposal will undergo QOL assessment using the RAND-36 Health Status Inventory³⁵ and the Minnesota Living with heart Failure Questionnaire³⁶ (Appendices 1 and 2) at baseline and at the 6-month follow-up visit which could be conducted by phone. Procedural information and complications as well as clinical events will be collected on patients enrolled in the non-randomized observational cohort, similarly to patients enrolled in Aim 1. Data on cost of care will also be collected for all patients enrolled in Aim 2.

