9 STATISTICAL CONSIDERATIONS

9.1 STATISTICAL AND ANALYTICAL PLANS

Randomized Aim

Descriptive patient characteristics will be presented as mean (SD) for continuous variables and n (%) for categorical variables. Baseline comparisons of patients assigned to CRT-P vs. CRT-D will be performed using t-tests for continuous variables (Wilcoxon rank-sum test if non-normally distributed) and chi-squared tests for categorical variables (Fisher’s Exact Test in case of small sample sizes within cells) to confirm that the randomized treatment arms are balanced in key demographics and potential confounders. The proportion of patients experiencing major/minor procedural complications within 30 days will be reported as n (%) within each treatment arm. These complication rates will be ascertained through review of pertinent medical records following the device implantation. Mortality [as n (%)] and the 6-month QOL outcomes [as mean (SD)] within each treatment arm will be reported as well. Cost of care for the index hospitalization for CRT device implantation and for the follow-up period will be measured at the conclusion of the study and compared between the 2 cohorts using a 2-sample t-test (or Wilcoxon test if the data are non-normally distributed). Retention will be presented as n (%) completing at least 6-month of follow-up. In addition to the retention, in order to document the recruitment success, we will report the number of patients approached in order to successfully enroll n=50 patients, which will be useful information in planning a large scale trial.

Observational Aim

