9.3 STUDY PITFALLS AND SUGGESTED SOLUTIONS

Randomized Aim

Based on the total volume of CRT recipients at the 4 enrolling institutions and the estimated percentage of acceptance of patients to enroll in a randomized CRT-P versus CRT-D trial provided by the physician (Appendix 1) and patient (Appendix 2) surveys, it is anticipated that the actual enrollment rate will exceed the rate needed to reach the target sample size of 50 patients in Aim 1 over a 1.25-year enrollment period. The required threshold for the rate of enrollment is 0.83 patients per institution per month. If the actual enrollment rate turns out to be slower than expected, then more institutions may be added to the pilot trial. The data gathered from this pilot trial will be necessary to inform the design of a future large, non-inferiority, randomized trial of CRT-P versus CRT-D with respect to number of sites needed and duration of the enrollment phase.

The present pilot randomized trial is by necessity un-blinded, i.e. patients and physicians know whether the implanted device is a CRT-P or CRT-D. In order to better understand if there are biases in the type of patients who accept randomization, the research is to be conducted as described in Aim 2 by doing so this will provide insight into the determinants of accepting participation in the randomized trial (compare patients in Aim 1 versus Aim 2) as well as insights into the determinants of choosing a CRT-P versus CRT-D device (compare patients in Aim 2 who received CRT-P versus CRT-D).

Observational Aim

The sample size needed for Aim 2 is likely to be easily achieved as we will offer enrollment to all patients screened but not enrolled into Aim 1. We expect the patient acceptance to enroll in an observational study where no clinical decisions are imposed by the research protocol to be very high. If our estimates of enrollment turn out to be too optimistic however, we would consider adding another institution to the research protocol to mitigate this issue.

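### Section 9.1 reports Aim 1 mortality as a crude n (%) with no time point, although length of follow-up differs between patients; a fixed-time estimate should be added

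*Combined protocol and SAP*

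**What the plan says.** For the randomized aim, Section 9.1 states: "Mortality [as n (%)] and the 6-month QOL outcomes [as mean (SD)] within each treatment arm will be reported as well". The same paragraph gives a horizon to the neighbouring outcomes: 30 days for procedural complications, 6 months for quality of life and for retention. Mortality has none. No survival-curve, person-time or censoring method appears anywhere in the plan.

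Follow-up does not have a fixed length. Section 6 says: "Patients will be followed in the pilot randomized trial from the date of enrollment until study closure". Its call schedule continues "every 6 months thereafter until the end of the study". Section 9.3 plans to recruit the 50 patients "over a 1.25-year enrollment period".

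The protocol synopsis gives the study duration as "Approximately 24 months" and the participant duration as "Up to 18 months from enrollment".

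On loss to follow-up, Section 5.5 ends study activities for patients who are withdrawn. It allows the Social Security Death Index as an adjunct when neither patient nor family can be reached. Section 6 lets next of kin report events at the scheduled calls.

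**The concern.** A percentage dead means something only over a stated period. With staggered entry and a common closing date, early entrants have longer to die than late entrants. The reported percentage then reflects the accrual calendar as well as the death rate, and it would change if recruitment ran faster or slower at the same hazard.

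A simple n/N also treats everyone not known to be dead as a survivor, including patients who left contact early.

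What is at stake is how the figure can be read. Section 4.1 says that the pilot was designed to mimic a future non-inferiority trial on total mortality and quality of life. A mortality percentage by arm from such a pilot is likely to be read next to figures from other studies, and without a horizon it cannot be compared with them.

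**Working it through.** **Inputs.** 50 patients (Section 9.2); "Total of four participating sites" and about 24 months' study duration (synopsis); 1.25 years = 15 months of accrual (Section 9.3); an 18-month participant limit (synopsis). The documents give no mortality rate, so 12-month mortality of 5% to 20% is assumed, with constant hazard and uniform accrual. The allocation ratio is not stated; 1:1, about 25 per arm, is assumed.

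**Step 1: reproduce the plan's own figure.** Section 9.3 states: "The required threshold for the rate of enrollment is 0.83 patients per institution per month". Check: 50 / (4 × 15) = 0.833. It reproduces, which confirms the 15-month accrual window.

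**Step 2: potential follow-up.**
- Reading A, closure at 24 months and no individual limit: last entrant 24 − 15 = 9 months, first entrant 24 months. Range 9–24, mean 16.5.
- Reading B, closure at 24 months, each patient limited to 18: range 9–18, mean 15.3; (24 − 18)/15 = 40% of patients reach the limit.
- Reading C, common closure at 18 months: last entrant 18 − 15 = 3 months. Range 3–18, mean 10.5.

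The longest follow-up is 24/9 = 2.7, 18/9 = 2.0 or 18/3 = 6.0 times the shortest. It varies under every reading.

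**Step 3: expected crude percentage.** With 12-month mortality m, the monthly hazard is h = −ln(1 − m)/12. For follow-up uniform on (a, b), the expected proportion dead is 1 − (e^(−ha) − e^(−hb)) / (h(b − a)).

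Worked case, m = 15%: h = 0.1625/12 = 0.01354.
- A: 1 − (0.8852 − 0.7225)/(0.01354 × 15) = 19.9%.
- B: 1 − [(0.8852 − 0.7837)/0.01354 + 6 × 0.7837]/15 = 18.6%.
- C: 1 − (0.9602 − 0.7837)/(0.01354 × 15) = 13.1%.

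| Assumed 12-month mortality | A: 9–24 | B: 9–18 | C: 3–18 |
|---|---|---|---|
| 5% | 6.8% | 6.3% | 4.4% |
| 10% | 13.4% | 12.5% | 8.7% |
| 15% | 19.9% | 18.6% | 13.1% |
| 20% | 26.2% | 24.6% | 17.5% |
| Ratio to 12-month mortality | 1.31–1.36 | 1.23–1.26 | 0.87 |

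**Step 4: mixing within one calendar.** At m = 15%, a patient's own risk of death over potential follow-up runs from 11.5% to 27.8% (A), 11.5% to 21.6% (B) or 4.0% to 21.6% (C). The crude percentage averages over that range.

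**Step 5: loss to follow-up, an unfavourable illustration.** Take reading A at m = 15%. Assume that 20% of patients leave contact at 6 months (the complement of the 80% retention used as an example in Section 9.2) and that none of their later deaths is found. Six-month mortality is 7.8%, so the expected figure is 0.8 × 19.9% + 0.2 × 7.8% = 17.5% instead of 19.9%. Next-of-kin contact and the death index would make the real loss smaller.

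**Step 6: precision.** For 3 deaths in 25 patients (12%), the exact 95% CI is 2.5% to 31.2%. For 7 in 50 (14%), it is 5.8% to 26.7%.

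**The case against.** Mortality is one descriptive line, with no test, in a feasibility pilot. Randomization blocked by site should give both arms similar follow-up, so the comparison between arms is largely protected. Sampling error is larger than the horizon effect. At 15%, reading B implies about 4.7 deaths in 25 against 3.75 at a fixed 12 months, roughly one death per arm. A Kaplan-Meier estimate would fix the horizon but not the imprecision. All of this stands and limits the point to a minor one.

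Three stronger readings are tempting and do not hold.
- A reader might infer that the pilot's mortality is meant to be the event rate for the pivotal trial. The documents do not say so. The quantities named as inputs are screening, acceptance, randomization, implantation and retention (Section 4.1), recruitment success and retention (Section 9.2), and number of sites and length of enrollment (Section 9.3). Section 8 does call all-cause mortality a primary endpoint, but in describing how the monitoring board may stop the trial. That is a separate inconsistency.
- A reader might take 9 to 24 months as settled. The synopsis's 18-month limit contradicts it.
- A reader might take the ratio between the highest and lowest columns, 19.9/13.1 = 1.5, as the error in the reported percentage. Those are alternative calendars, of which only one can occur. The relevant comparison is crude against fixed-time mortality within one calendar, the last row of the table.

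It is also fair to say that lost patients are not simply assumed alive, because the next-of-kin and death-index routes recover some deaths. They do not make the denominator or the horizon explicit.

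**Conclusion.** The concern holds as a minor reporting defect. Planned Aim 1 mortality has no defined time horizon, and undetected deaths among lost patients would count as survival. Under the assumed constant hazard, uniform accrual and 12-month mortality of 5% to 20%, the expected crude figure is 1.31 to 1.36 times, 1.23 to 1.26 times or 0.87 times the 12-month mortality, depending on which follow-up reading applies. Even the direction of the difference is therefore unsettled until the follow-up statements in the synopsis and in Sections 6 and 9.3 are reconciled. Nothing here suggests material bias between the arms, and the pilot's stated feasibility aims are unaffected. The figure would mislead only if it were taken as a 12-month rate or carried into planning of the pivotal trial.

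**What to change.** In Section 9.1, keep the death counts per arm and add for Aim 1:
- Kaplan-Meier mortality at 6 and 12 months from randomization, by arm, with 95% CI and numbers at risk, censoring at the date last known alive;
- deaths per person-year;
- median follow-up per arm.

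Numbers at risk matter because under reading C only (18 − 12)/15 = 40% of patients could reach 12 months, against (18 − 6)/15 = 80% for 6 months. Under readings A and B, (24 − 12)/15 = 80% could reach 12 months.

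Reconcile the synopsis's participant duration with follow-up to study closure in Section 6 and the calendar in Section 9.3.

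The change should stay within Aim 1. Section 9.1 plans no mortality summary for the observational cohort. Section 5.3 lets those patients enroll up to 14 days after implant, so counting from enrollment could miss early procedural deaths.

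The cost is a few lines of analysis text and slightly more analysis. The documents list death and survival as collected events but name no field for date of death or date last known alive. The sponsor must confirm that the CRF captures both; if it does not, a CRF change is also needed.

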4.2 STUDY ENDPOINTS

4.2.1 PRIMARY ENDPOINT

With the Aim 1 randomized subjects the primary endpoint is the ability to enroll in the randomized controlled trial of CRT-P versus CRT-D patients. The subjects enrolled with aid in determining and assessing feasibility of screening, enrolling, randomizing, and retaining participants in this pilot trial.

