5.5 PARTICIPANT WITHDRAWAL OR TERMINATION

During the consenting process subjects will be informed of their rights to withdraw from the study at any time without prejudice. Subjects who no longer attend their required in-office follow-up or are unable to be reached by telephone after 2 documented attempts by investigator, will be considered lost to follow-up. These subjects will not undergo any additional study activities once they have been withdrawn. The Social Security Death Index³⁷ will only be used as an adjunctive method of confirming death if no contact at all could be established with the patient or family during follow-up. Any identifiable research or medical record information recorded for, or resulting from, the subject's participation in this research study prior to the date that they formally withdraw consent may continue to be used and disclosed by the investigators for research purposes.

A patient may be discontinued from participating in this research if their device implantation procedure is not successful or is complicated by death or if they fail to follow-up after device implantation according to the research protocol requirements.

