9.2 SAMPLE SIZE

Randomized Aim

It will be of interest to estimate the recruitment success rate and the retention rate in this population, as that will be useful knowledge for designing a pivotal non-inferiority trial. The proposed sample size of 50 patients guarantees a maximum sample standard deviation = $\sqrt{(.5*(1-.5)/50)} = 7\%$, meaning that a 95% confidence interval will have a maximum margin of error $\pm 13\%$ in estimating true retention rate. However, this margin-of-error may be lower (the further the sample retention is from 50%). For example, if 40/50=80% participants enrolled complete at least the 6-month visit, a 95% CI estimating the true 6-month retention in this population would range from 68.9-91.1%, information that can be used to guide recruitment estimates for the large scale trial. The recruitment success rate can be estimated with even more precision, as there will be a larger N approached than N enrolled (and thus a smaller standard deviation of the sample proportion).

Observational Aim

It is anticipated based on the physician and patient surveys that approximately 40% of patients offered the opportunity to enroll in the pilot randomized controlled trial of Aim 1 will do so. Therefore, 125 patients will need to be screened to enroll 50 in the pilot randomized trial. It is assumed that 80% of those who decline participation in Aim 1 will agree to be followed in the observational cohort, the cohort will consist of 60 non-randomized patients. A comparison will be scored on the Satisfaction with Decision Scale using a t-test (or Wilcoxon rank-sum test, if non-normally distributed). Assuming roughly equal numbers select CRT-D vs. CRT-P, enrollment of 60 cohort participants will have 80% power to detect a difference in Satisfaction with Decision scores if one treatment group's average score is at least 0.75 standard deviations higher than the other group.

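### Aim 1 retention has no rule for deaths, and Section 5.5 lets randomized patients leave research follow-up that Section 6 continues to study closure

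*Combined protocol and SAP*

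**What the plan says.** Section 4.2.1 names the ability to enroll as the primary endpoint and explains that the enrolled subjects serve for "assessing feasibility of screening, enrolling, randomizing, and retaining participants in this pilot trial". Section 3 includes maintaining patients in the trial in the primary objective.

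The analysis of retention is one sentence in Section 9.1 (Randomized Aim): "Retention will be presented as n (%) completing at least 6-month of follow-up". That sentence gives no denominator and does not mention deaths. Section 9.2 supplies an example, "if 40/50=80% participants enrolled complete at least the 6-month visit", with a 95% interval of 68.9% to 91.1%, and describes the result as "information that can be used to guide recruitment estimates for the large scale trial". Mortality is reported by arm in Section 9.1 as n (%), without a time point.

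Section 5.5 sets the rules for leaving the study:

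- "A patient may be discontinued from participating in this research if their device implantation procedure is not successful or is complicated by death"; the same sentence adds failure to follow up after implantation.
- The loss rule covers patients who miss the required visits, and those "unable to be reached by telephone after 2 documented attempts by investigator, will be considered lost to follow-up".
- The section then states what follows for such patients: "These subjects will not undergo any additional study activities once they have been withdrawn".

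Section 6 (Randomization Aim) says: "Patients will be followed in the pilot randomized trial from the date of enrollment until study closure". It makes no exception for the cases in Section 5.5, and schedules telephone contact at 30 days, 3 months, 6 months and every 6 months after that.

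**The concern.** The pilot is meant to mimic a pivotal non-inferiority trial whose outcomes are total mortality and quality of life (Section 4.1). A dated death is complete data for the first outcome and leaves no score for the second. A single percentage that puts deaths together with lost contact does not show how complete either outcome would be. Section 2.1 itself says that older patients carry a higher risk of death. The authors deal with deaths explicitly in Aim 2, where a deceased patient is given the lowest satisfaction score, but state no such rule for retention in Aim 1.

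The second part concerns how the losses arise. If a randomized patient can be dropped from the research because the implant failed, part of the attrition is produced by the protocol. That loss happens after randomization and depends on the outcome of the procedure. It would lower the figure the pilot sets out to measure, and would leave data missing for patients whose course is of particular interest.

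**Working it through.** **1. The protocol's own figure.** Inputs from Section 9.2: 40 completers, 50 enrolled, 95% confidence. With the Wald formula, p ± 1.96 × √(p(1−p)/n):

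0.80 ± 1.96 × √(0.80 × 0.20 / 50) = 0.80 ± 1.96 × 0.0566 = 0.80 ± 0.111, or 68.9% to 91.1%.

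This matches the protocol. It confirms that the denominator in the example is all enrolled and that the half-width is 11.1 points.

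**2. Where a death falls.** A patient who dies before 6 months cannot be among those who complete the 6-month visit. No section removes such a patient from the 50 or counts the patient as complete. By the definition and the example together, the death is one of the 10 non-completers.

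**3. What the 80% can conceal.** The documents give no 6-month death rate, so the number of deaths d among the 10 non-completers is an assumption. Known vital status is (40+d)/50. It is a lower bound, because some surviving non-completers may also have known status. Completion among survivors is 40/(50−d). Non-completion for reasons other than death is (10−d)/50. Intervals are Wald.

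| d (assumed) | As written | Vital status known, at least | Completion among survivors | Non-completion other than death |
|---|---|---|---|---|
| 0 | 40/50 = 80% | 40/50 = 80% | 40/50 = 80% | 20% |
| 2 | 80% | 42/50 = 84.0% (73.8–94.2) | 40/48 = 83.3% (72.8–93.9) | 16% |
| 5 | 80% | 45/50 = 90.0% (81.7–98.3) | 40/45 = 88.9% (79.7–98.1) | 10% |

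For d from 2 to 5, the shift from 80% is 4 to 10 points for vital status and 3.3 to 8.9 points for completion among survivors. All of these are smaller than 11.1 points. Completion among survivors equals quality-of-life completion only if every completer returned the questionnaires.

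**4. Sections 5.5 and 6 side by side.** Section 6 follows every randomized patient to closure. Section 5.5 permits, but does not require, discontinuation from the research after an unsuccessful implant or missed follow-up. It also classes a patient as lost after two failed telephone attempts and ends study activities for those withdrawn. It does not say whether being lost equals being withdrawn, or whether the two attempts are counted per scheduled call. On the strictest reading, a patient lost at the 30-day call would not be called at 3 or 6 months, which are 2 of the 3 contacts up to 6 months. On a looser reading, contact is tried again. The text does not settle which is meant.

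**5. Can every patient reach 6 months?** The synopsis gives a study duration of about 24 months and a participant duration of up to 18 months. Section 9.3 gives 1.25 years of enrollment, which is 15 months.

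- If enrollment opens at month 0 and the study closes at month 24, the last patient has about 24 − 15 = 9 months.
- If 18 months is the first patient's maximum up to a common closure, the last patient has about 18 − 15 = 3 months.

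The second case falls short of 6 months, and the plan does not say how a patient censored by closure would enter retention.

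**The case against.** The strongest reply is that this is a descriptive figure in a 50-patient pilot, with no test and no threshold attached to retention. Section 4.2.1 makes ability to enroll the headline endpoint. Deaths are not hidden: they are sought from next of kin at the scheduled calls (Section 6), recorded on serious adverse event forms (Section 7.2), checked in the Social Security Death Index when no contact at all can be made (Section 5.5), and reported by arm (Section 9.1). Procedural complications within 30 days come from medical records. Discontinuation after a failed implant is only permitted, and Section 5.4 calls the two procedures similar in duration and risk, so any such loss may be balanced between arms. For quality of life, an all-enrolled completion figure is a reasonable planning number.

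Most of this stands, and it limits the point. The split by cause could be recovered from the data collected; what is missing is a plan to report it. The death index does not supply quality-of-life scores. None of the reply resolves the conflict between Sections 5.5 and 6.

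A reader might go further and infer that the retention figure would make the pivotal trial too large. The documents do not support that. It would require an assumed number of deaths and an assumption that planners divide by retention while ignoring the mortality reported beside it. Nor do they support concluding that patients are never called again after two failed attempts, which is only one reading of unclear text.

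**Conclusion.** The point holds as a gap in definition together with a conflict between two sections. As written, a death before 6 months counts as not retained, because the plan has no rule for it. Section 5.5 allows loss after randomization that depends on the procedure's outcome, against Section 6.

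The size is unknown. The shifts of 3.3 to 10 points rest on an assumed 2 to 5 deaths among 10 non-completers; with no deaths they vanish. They lie within the sampling error of the example. The difference is nevertheless in what is being measured, so a larger sample would not remove it. No rate is given from which to size the loss after failed implants.

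A reader might take the 24-month duration to mean that every patient is observed for at least 6 months. The 18-month participant duration prevents that conclusion: minimum follow-up could be about 3 to 9 months. The change is worth making because it is cheap and bears on a quantity the pilot exists to measure. It does not call the design or the sample size into question.

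**What to change.** 1. Reconcile Sections 5.5 and 6 so that all randomized patients stay in research follow-up in their assigned arm whatever the implant outcome, unless consent is withdrawn. State that a patient not reached is tried again at the next scheduled call. This concerns research follow-up only, not treatment.
2. In Section 9.1, keep the stated retention figure with all randomized patients as the denominator. Add (a) vital status known at 6 months, with known deaths counted as ascertained, and (b) 6-month quality-of-life completion among those alive at 6 months.
3. List by arm the deaths, consent withdrawals, discontinuations, losses to follow-up and any patients not yet at 6 months when the study closes.
4. Report mortality at 6 months.
5. Reconcile the 24-month study duration, the 18-month participant duration and the 15-month enrollment period. If minimum follow-up is below 6 months, do not count patients censored by closure as not retained; show their number separately.

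The cost is revised wording in the synopsis and Sections 5.5, 6, 9.1 and 9.3, a few more telephone calls and slightly more reporting. No additional patients or procedures are needed.
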